## 3.5.2. Cohort Stopping Rules

If any of the following safety concerns are observed, dosing of all subjects at the given dose level or higher will be suspended/halted and all available data will be evaluated by the DSMB.

Dose continuation (remaining subjects within a cohort or remaining dosing for a subject) or escalation should not proceed for any of, but not limited to, the following reasons:

- If one SBP-9330-related SAE occurs in a cohort
- Severe AE at least possibly related to SBP-9330 in two or more subjects in the same cohort\*
- Other findings that, at the discretion of the DSMB or Sponsor, indicate further dosing should be stopped

\* Prior to suspending the cohort, if severe AEs are reported in two or more subjects at a given dose level, consideration should be given to the treatment assignment (SBP-9330 or placebo). After causality assessment, the Investigator (or designee) should open the individual randomization code to verify the treatment received. Dosing at the given dose level may continue if only one subject received SBP-9330 and the other(s) received the placebo.

Subjects experiencing severe AEs will be followed up with serial measurements of the related clinical parameter(s), as per medical judgment, until resolution, stabilization, or until the subject is lost to follow-up.

Dose escalation will be discussed during the DSMB meeting and may be stopped depending on Principal Investigator's or Sponsor's decision, based on but not limited to the following:

- New clinically significant abnormalities in physical examination, 12-lead ECG, or vital signs in two or more subjects
- Overall pattern of clinical changes or symptoms that may have appeared minor in terms of an individual AE or subject, but which collectively present a safety concern
- Clinically significant changes in organ-specific laboratory parameters (e.g., liver function enzymes in one or more subjects)
- Pattern of laboratory changes (e.g., a consistent increase or decrease in two or more subjects or within or across dosing cohorts) that might indicate an overall safety concern

In addition to the safety stopping criteria listed above, dose-escalation PK stopping criteria will be implemented such that systemic exposures in subjects do not exceed  $1/10^{th}$  of the  $AUC_{0-24hr}$  and  $C_{max}$  levels associated with the identified NOAEL of the GLP 14-day rat study. The  $1/10^{th}$  stopping values for  $C_{max}$  and  $AUC_{0-24hr}$  are 25.4  $\mu g/mL$  and 224  $\mu g^*$  hr/mL, respectively. Dose escalation in the SAD, MAD, or Smoker components of the study will be stopped before these exposures are achieved.

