#### 3.3.1. Part A – SAD Phase with Nested Food-Effect Cohort

Screening of participants will occur within approximately 28 days of the first scheduled administration of study medication. Screening data will be reviewed to determine subject eligibility. Subjects who meet all inclusion criteria and none of the exclusion criteria and who

Altasciences Project Number: CNO-P5-319

consent to participation will be admitted to the CRU for baseline evaluations before dosing (Day -1). All baseline safety evaluation results should be available prior to dosing and continued eligibility confirmed. Subjects in Cohort A3 will have eligibility confirmed for Day -1 for fasted dose (Period 1) only and not for the fed dose (Period 2).

Eligible subjects will be randomized to SBP-9330 or placebo in 1 of the 5 ascending dose cohorts (8 subjects per cohort) to have a total of 6 subjects receiving SBP-9330 and 2 subjects receiving placebo. All cohorts in the fasting state will be dosed according to a sentinel dosing design to ensure optimal safety. Initially, 2 subjects will be dosed; 1 subject will be dosed with SBP-9330 and 1 subject with placebo. If the safety and tolerability results of the first 24 hours following dosing for the initial subjects are acceptable to the Investigator, the other 6 subjects (5 active and 1 placebo) may be dosed approximately 24 hours after dosing of the sentinel group.

Furthermore, one single-dose, two-period, crossover, food-effect cohort will be integrated into a SAD cohort (Cohort A3).

The proposed SAD design and planned escalation are presented in Table 7.

Altasciences Project Number: CNO-P5-319

Table 7 Part A – SAD Phase with Nested Food-Effect Cohort Design and Dose Levels

Cohort	N (active:placebo)	Dose (mg)	Drug administration
A1	6:2 (1:1 [sentinel group] and 5:1 [remaining subjects])	150 mg (1 × 150-mg SBP-9330 capsule or matched placebo)	Single oral dose administration of SBP-9330 or placebo under fasting conditions on Day 1.
A2	6:2 (1:1 [sentinel group] and 5:1 [remaining subjects])	300 mg (1 × 300-mg SBP-9330 capsule or matched placebo)	Single oral dose administration of SBP-9330 or placebo under fasting conditions on Day 1.

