## 5.2.3. Method of Assigning Subjects to Treatment Groups

The CRU will generate the randomization code for each cohort with a computer program according to the study design, the number of subjects and the treatment to be administered. Once generated, the randomization code will be final and will not be modified.

Subjects enrolled in the SAD sentinel groups will be randomized 1:1 to receive SBP-9330 or matching placebo while the rest of the subjects in the cohort will be randomized 5:1 to receive SBP-9330 or matching placebo. Subjects enrolled in the MAD and Smoker cohorts will be randomized 8:2 to receive SBP-9330 or matching placebo.

Subjects who sign the informed consent form (ICF) and are randomized but do not receive the study treatment may be replaced. Subjects who sign the ICF, are randomized and received at least 1 dose of the study treatment, and are withdrawn prematurely from the study, may be replaced by an equal number of newly enrolled subjects. A new unique randomization number

Altasciences Project Number: CNO-P5-319

will be assigned to the replacement subject. The replacement list will be provided and will be identical to the original randomization scheme.

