# 5.2.4. Blinding

This study is double-blind. Treatment assignments (active or placebo) will be blinded to the investigator, subjects and all clinical and research staff for the entire study, with the exception of designated pharmacy staff who will remain unblinded in order to dispense active drug or placebo.

The study blind will be broken upon completion of the clinical study and after the study database has been locked.

During the study, the randomization code must not be broken except in emergency situations where the identification of a subject's study treatment is required by the qualified investigator for further treatment to the subject, to assess cohort stopping rules or to complete a SAE report. Randomization information will be held by designated individual(s). When possible, the qualified investigator should discuss the emergency with the Sponsor prior to unblinding. The date and reason for breaking the blind must be recorded.

The results of the blinded safety and available PK data will be made available to the DSMB group before proceeding with the next dose level. The DSMB will be provided the randomization code to aide in the review for Part C. The bioanalytical facility will preserve the blind by reassigning alternative subject numbers to the interim data before they are made available to the PK facility and Sponsor; these alternative subject numbers will be assigned by the lab at the time of sample analysis. For the food-effect cohort (Cohort A3), the clinic will provide the lab with the meal condition for each subject, and the lab will translate this information to the corresponding alternative subject number and will provide the resulting list comprised of alternative number and associated meal condition to the PK scientist. These measures will ensure that whenever possible, the DSMB members remain blinded during their reviews and throughout the clinical part of the study. Based on review of the safety data, the DSMB may request randomization information, if necessary, to make appropriate dose escalation decisions and this unblinding will be documented.

At the request of the Sponsor, specified individuals may be unblinded and receive the randomization information prior to database lock. This unblinding will be fully documented and all unblinded individuals advised that they must not distribute randomization information to any blinded parties.

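### The severe-AE check in Protocol 3.5.2 gives opened codes to the Investigator who keeps rating that cohort, and in SAD cohorts it can also reveal subjects whose codes stayed closed

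*Protocol*

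**What the plan says.** Protocol 3.5.2 halts dosing at a dose level on several grounds. One is: "Severe AE at least possibly related to SBP-9330 in two or more subjects in the same cohort". A footnote to that bullet adds a step before suspension. It applies "if severe AEs are reported in two or more subjects at a given dose level" and reads: "After causality assessment, the Investigator (or designee) should open the individual randomization code to verify the treatment received". The release condition follows: "Dosing at the given dose level may continue if only one subject received SBP-9330 and the other(s) received the placebo".

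Protocol 5.2.4 sets the general rule: "Treatment assignments (active or placebo) will be blinded to the investigator, subjects and all clinical and research staff for the entire study". Designated pharmacy staff are the stated exception. The same section allows the code to be broken for a subject's treatment and also "to assess cohort stopping rules or to complete a SAE report". SAP 3.5 repeats both the rule and the exceptions.

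The SAD allocation is fixed in two groups. For the sentinels, Protocol 3.3.1 says: "Initially, 2 subjects will be dosed; 1 subject will be dosed with SBP-9330 and 1 subject with placebo". For the other six, Protocol 5.2.3 says that "the rest of the subjects in the cohort will be randomized 5:1 to receive SBP-9330 or matching placebo". MAD and Smoker cohorts are randomized 8:2 with no sentinel split.

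Neither document says who the designee in the footnote is, whether the result is kept from the Investigator, or what an opened code implies about other subjects.

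**The concern.** The footnote treats the code-break as a matter for the affected subjects only. In a SAD cohort it need not be. A sentinel's code gives away the other sentinel, and the placebo code among the six gives away five actives.

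The person who learns this is the Investigator, who assigns causality to every AE (Protocol 7.3) and judges which abnormal laboratory values count as AEs (6.1.5). AE incidence and severity are the primary endpoint (8.3.1). The triggering events are rated before the codes are opened, but AE collection runs to the follow-up visit (7.4). In Cohort A3 the same subjects receive the same assignment again in Period 2, so a Period 1 code-break would carry into the fed-period ratings. In MAD and Smoker cohorts the opened subjects may have up to 13 dosing days left.

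There is also a wording gap. The bullet requires relatedness and a shared cohort. The footnote's count clause mentions neither and refers to a dose level. Protocol Table 6 allows an equivalent dose in a later cohort, so cohort and dose level need not coincide. Read literally, the release sentence also omits the case where every affected subject received placebo.

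**Working it through.** **Inputs.** SAD cohort: 2 sentinels (1 active, 1 placebo) and 6 others (5 active, 1 placebo), from Protocol 3.3.1 and 5.2.3. MAD and Smoker cohorts: 8 active, 2 placebo, from 5.2.3.

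**Plan's own figure.** 1 + 5 = 6 active and 1 + 1 = 2 placebo, which reproduces the stated 6:2.

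**Rule for counting.** There are 2 × 6 = 12 possible allocations. An unopened subject counts as revealed if every allocation consistent with the opened codes gives that subject the same treatment. Two opened codes give C(8,2) = 28 pairs.

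**By position of the pair**

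| Opened pair | Pairs | Pairs revealing someone else | Others revealed |
|---|---|---|---|
| Both sentinels | 1 | 0 | 0 |
| One sentinel, one of the six | 12 | 12 | 1 in ten pairs, 6 in two pairs |
| Both among the six | 15 | 5 | 4 each |
| Total | 28 | 17 (60.7%) | |

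**By result of the pair**

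- One active, one placebo: 6 × 2 = 12 pairs. Both sentinels, 1 pair, 0 revealed. Sentinel placebo with an active from the six, 5 pairs, 1 revealed. Both among the six, 5 pairs, 4 revealed. Sentinel active with the placebo from the six, 1 pair, 6 revealed. At least one revealed: 11/12 (92%). Mean known treatments: 2 + (0×1 + 1×5 + 4×5 + 6×1)/12 = 2 + 31/12 = 4.6 of 8.
- Both active: C(6,2) = 15 pairs. Five include the active sentinel and so reveal the other sentinel: 5/15 (33%).
- Both placebo: 1 pair, all 6 others revealed.
- Check: 11 + 5 + 1 = 17.

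**Comparison.** One block of eight at 6:2 without the split would reveal someone in 1 of 28 pairs (3.6%). At 8:2, the figure is 1 of C(10,2) = 45 (2.2%), the pair of both placebos. After one active and one placebo code at 8:2, the remaining eight are 7:1 and nobody else is certain.

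**If the Investigator hears only that the release condition is met.** With both affected subjects among the six (5 of the 12 release pairs), one of them must hold the only placebo there, so the other four are known to be active. In the other 7 pairs the message makes no treatment certain. Mean known: 5 × 4/12 = 1.7 of 8, against 4.6.

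**If the Investigator hears that it is not met.** With two affected subjects, both must be active, which is what opening both codes would show.

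**How often.** The documents give no AE rates. As an illustration, assume independent subjects with severe, at least possibly related AE rates of 5–10% on active and 1–2% on placebo. Exactly one active and at least one placebo affected in a SAD cohort:

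- Low: 6 × 0.05 × 0.95⁵ × (1 − 0.99²) = 0.232 × 0.0199 = 0.5%
- High: 6 × 0.10 × 0.90⁵ × (1 − 0.98²) = 0.354 × 0.0396 = 1.4%

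Over five cohorts this is 1 − (1 − 0.0046)⁵ = 2% to 1 − (1 − 0.0140)⁵ = 7%.

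**The case against.** A reader might infer that 3.5.2 contradicts 5.2.4. It does not: 5.2.4 names cohort stopping rules as a reason to break the code, and the footnote uses that exception. The footnote also allows a designee.

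A reader might also infer that any code-break exposes the rest of the cohort. That is too strong. In 11 of 28 pairs nobody else becomes certain, including 10 of the 15 both-active pairs, which are the ones the stopping rule is aimed at.

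The count of 12 release pairs gives each pair equal weight. The six are dosed only if the sentinels' first 24 hours are acceptable, so a pair joining a sentinel with one of the six needs a later sentinel event or a decision to go ahead despite one. In the single-dose cohorts little dosing may remain at that level once two of the six are affected. The harm is bounded: triggering AEs are rated first, subjects are not told, AEs are elicited by open questions, and the primary endpoint is incidence and severity rather than causality. SAP Table 8 counts events rated unlikely as drug-related, so that table changes only if a rating moves to or from not related.

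All of this stands and limits the point. It does not explain why the AE assessor should hold the result when unblinded pharmacy staff are available. An unnamed designee gives no assurance that the result is kept from the Investigator. The footnote's asterisk supports reading it together with its bullet, but the text does not say so.

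**Conclusion.** The point holds as a minor one. A permitted code-break is sent to the person who continues to rate AEs in that cohort, and in SAD cohorts it can reveal unopened subjects. It does so whenever exactly one sentinel code, or the placebo code of the group of six, is opened.

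The shares of 61%, 92% and 33% describe the allocation given two opened codes, with every pair weighted equally and the sentinel gate ignored. It would be wrong to read 92% as the chance of unblinding in this trial. On the illustrative rates, the release case arises in about 0.5–1.4% of SAD cohorts.

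The exposure is confined to later ratings in the affected cohort, chiefly MAD and Smoker dosing days and A3 Period 2. A reader might infer that the decision to stop dosing is compromised. The documents do not support that, since relatedness is judged before the codes are opened. With two placebo subjects per cohort and descriptive analysis, the size of any rating bias could not be estimated from the trial.

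**What to change.** Replace the footnote with text to this effect:

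> If the criterion in this bullet is met in a cohort, then before suspension and after the Investigator's causality assessment, the unblinded pharmacist checks the treatment of the affected subjects. The pharmacist tells the Investigator only whether the release condition is met, namely that no more than one of them received SBP-9330 (including none). Subject-level treatment is given to the DSMB only. If the condition is met, whether dosing continues remains a medical judgement.

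In 5.2.4 and SAP 3.5, limit the stopping-rule exception to this route and leave the Investigator's emergency unblinding as it is. Tying the step to the bullet settles the relatedness and cohort wording, and the release condition now covers the all-placebo case.

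The cost is one footnote and one clause, the latter mirrored in the SAP, with no new staff or data. The pharmacist must be reachable the same day. The leak is reduced rather than removed. Release still shows the other four to be active when both affected subjects are among the six (5 of 12 pairs). Suspension with two affected subjects still tells the Investigator that both are active, and so identifies the other sentinel in 5 of those 15 pairs.

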All cohorts in the fasting state will be dosed according to a sentinel dosing design to ensure optimal safety. Initially, 2 subjects will be dosed; 1 subject will be dosed with SBP-9330 and 1 subject with placebo. If the safety and tolerability results of the first 24 hours following dosing for the initial subjects are acceptable to the Investigator, the other 6 subjects (5 active and 1 placebo) may be dosed approximately 24 hours after dosing of the sentinel group.

Escalation to the next higher dose will only proceed if none of the stopping criteria have been reached and when the safety and tolerability and available plasma PK analysis of the previous dose, including delayed significant AEs in earlier cohorts, are acceptable to the Investigator, Sponsor and Data and Safety Monitoring Board (DSMB).

The SAD Phase will have a maximum of 5 cohorts. The number of cohorts may be changed at the discretion of the Sponsor depending on the emerging safety and plasma PK data from the previous cohorts. The dose levels proposed for SAD cohorts may be adjusted during the course of the study based on preliminary safety and plasma PK data but escalation will not be more than 3-fold the previous dose.

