Abbreviations: CNS = central nervous system; hERG = human ether-à-go-go-related gene; GLP = good laboratory practice; NOAEL = no-observed-adverse-effect level

The high doses for the pivotal (GLP) repeat-dose rat and dog toxicity studies were chosen based on the maximum tolerated dose defined in the dose range-finding studies. At the highest dose in the pivotal (GLP) repeat-dose studies, toxicity was characterized by poor tolerability without specific organ toxicity. In the 14-day pivotal (GLP) toxicity study in rats, doses up to 600 mg/kg/day were well tolerated. Treatment-related findings were limited to minor clinical pathology alterations in glucose, albumin, total protein, A/G ratio, triglycerides and cholesterol (total and HDL), and liver, adrenal gland and spleen weight increases without histopathologic correlates. Based on these findings, the NOAEL of SBP-9330 in rats was determined to be 600 mg/kg/day. At 600 mg/kg/day, the systemic exposure (AUC) values on study day 14 were 635,000 and 2,240,000 hr.ng/mL for males and females, respectively.

In the SBP-9330-nicotine combination study, Wistar rats were administered different combinations of SBP-9330 vehicle or SBP-9330 at 60, 120, 300, and 600 mg/kg/day, followed by a subcutaneous injection of nicotine vehicle or nicotine at 0.3 mg/kg/day. No interactions between SBP-9330 and nicotine were observed in the toxicity or exposure of either SBP-9330 or nicotine. The toxicity of SBP-9330 in this combination study was similar to that observed in the 14-day definitive rat toxicity study with SBP-9330. The findings in this combination study included non-adverse increases in the mean liver to body weight ratios, minimal diffuse hepatocellular hypertrophy, increases in albumin, albumin to globulin ratios, cholesterol,

Altasciences Project Number: CNO-P5-319

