The SAD phase will have a maximum of 5 cohorts. The number of cohorts may be changed at the discretion of the Sponsor depending on the emerging safety and plasma PK data from the previous cohorts. The dose levels proposed for SAD cohorts may be adjusted during the course of the study based on preliminary safety and plasma PK data but escalation will not be more than 3-fold the previous dose.

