## **8.6.** Planned Interim Pharmacokinetic Analyses

Interim PK analysis may be performed after each cohort of the SAD, MAD, and Smoker phase for dose selection and safety assessment.

The SAP will describe the planned interim analyses in greater detail.

Altasciences Project Number: CNO-P5-319

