10 INTERIM ANALYSES AND DATA SAFETY MONITORING

Preliminary blinded “top line” PK results will be generated after each cohort of the SAD and MAD phase for dose selection and safety assessment prior to the next dose escalation.

These preliminary blinded PK results will be performed on SBP-9330 data as outlined in Sections 7.1 through 7.4, with the exception that nominal times will be used in the analysis instead of actual times. Blinded concentration tables, mean and blinded individual plasma concentration-time profiles, blinded PK parameter tables of the key PK endpoints (e.g., C_{max} , T_{max} , and AUCs) will be generated, data permitting.

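### The PK limit is written to stop escalation before it is reached, but Protocol 3.5 is worded as stopping once it has been reached and SAP 10 reports only observed exposures, with no projection to the next dose

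*Protocol*

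**What the plan says.** **The limit.** Protocol 3.5.2 intends that exposures in subjects stay at or below one tenth of the Cmax and AUC0-24 seen at the rat NOAEL. It gives 25.4 µg/mL and 224 µg·hr/mL, and adds: "Dose escalation in the SAD, MAD, or Smoker components of the study will be stopped before these exposures are achieved". Protocol 1.4 repeats the commitment without the figures.

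**The stop.** Protocol 3.5 stops escalation when the safety or tolerability limits, or the PK criteria of 3.5.2, are determined to have been reached.

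**The steps.** For Part A, "escalation will not be more than 3-fold the previous dose". Table 7 plans 150, 300, 600, 1200 and 2400 mg.

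**The interim output.** SAP 10 provides concentration tables, "mean and blinded individual plasma concentration-time profiles, blinded PK parameter tables of the key PK endpoints", for example Cmax, Tmax and AUCs. The work follows SAP 7.1 to 7.4. The power model is in 7.5.2, outside that range.

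**Whether interim PK is required.**
- Protocol 8.6: "Interim PK analysis may be performed after each cohort of the SAD, MAD, and Smoker phase for dose selection and safety assessment".
- SAP 10: results will be generated before the next escalation, for the SAD and MAD phases only.
- Protocol synopsis, Part A: escalation proceeds "when the safety and tolerability and available plasma PK analysis of the previous dose" is acceptable. The synopsis section on safety meetings and Protocol 3.2 likewise have the DSMB review whatever plasma PK is available.
- Protocol 3.3.1 and 3.5: the PK analysis of the previous dose must be acceptable to the Investigator, Sponsor and DSMB, with no qualifier about availability.

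**The concern.** A rule that stops escalation before an exposure is achieved concerns a dose not yet given. The specified outputs describe the dose just completed. If the reviewing parties ask only whether the limit has been reached, as 3.5 is worded, a cohort can pass and the next permitted dose can take subjects above the level that 3.5.2 says will not be exceeded. Following 3.5 and SAP 10 as written can therefore break 3.5.2.

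Two further gaps make the rule hard to apply. No passage names the statistic compared with the limit (highest individual, cohort mean or other). The documents also disagree on whether the PK analysis must be in hand before escalation, and SAP 10 omits the Smoker phase although 3.5.2 and 8.6 both cover it.

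At stake is the trial's only numeric exposure limit, in a first-in-human study with no earlier human PK (Protocol 1.2.3).

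**Working it through.** **1. Reproduce the plan's limit.** Protocol 1.2.2 reports that at the rat NOAEL "the systemic exposure (AUC) values on study day 14 were 635,000 and 2,240,000 hr.ng/mL for males and females, respectively".
- Female: 2,240,000 / 10 = 224,000 ng·hr/mL = 224 µg·hr/mL, which matches 3.5.2.
- Male: 635,000 / 10 = 63,500 ng·hr/mL = 63.5 µg·hr/mL.

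The AUC limit rests on the female value. The Cmax limit implies 25.4 × 10 = 254 µg/mL at the NOAEL. The documents do not give that figure, so it cannot be checked.

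**2. Step sizes.** 300/150 = 600/300 = 1200/600 = 2400/1200 = 2. The permitted maximum is 3.

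**3. Project one step.** Next exposure = current exposure × fold^slope. The slope is not in the documents; I assume 1.0 and show 0.8 to 1.2. A cohort at or above 100/fold^slope percent of the limit, but below 100%, shows no breach and projects to or above the limit.

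| Step | Slope | Multiplier | Lower edge, % of limit | Cmax (µg/mL) | AUC0-24 (µg·hr/mL) |
|---|---|---|---|---|---|
| 2-fold | 0.8 | 1.74 | 57 | 14.6 | 128.7 |
| 2-fold | 1.0 | 2.00 | 50 | 12.7 | 112.0 |
| 2-fold | 1.2 | 2.30 | 44 | 11.1 | 97.5 |
| 3-fold | 0.8 | 2.41 | 42 | 10.6 | 93.0 |
| 3-fold | 1.0 | 3.00 | 33 | 8.5 | 74.7 |
| 3-fold | 1.2 | 3.74 | 27 | 6.8 | 59.9 |

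At slope 1, a cohort just under the limit would project to about Cmax 50.8 and AUC 448 after a 2-fold step, or 76.2 and 672 after a 3-fold step. These bands describe the gap; they are not proposed thresholds.

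**4. Illustrate with individuals.** Assume log-normal exposures, slope 1, geometric mean g (as a fraction of the limit) and between-subject CV. The CV is also not in the documents. Then s = √ln(1 + CV²), p = 1 − Φ(ln(1/g)/s), and the chance that at least one of 6 active subjects exceeds the limit is 1 − (1 − p)^6.

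Worked case, g = 0.5, CV 30%, 2-fold step: s = 0.294 and p = 0.009, so the chance that none of 6 exceeds now is 0.947. At the next dose g = 1 and p = 0.5, so the chance of at least one is 1 − 0.5^6 = 0.984. A clean cohort followed by a breach, if the step is taken: 0.947 × 0.984 = 0.93.

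| Current g | Step | CV 20% | CV 30% | CV 50% |
|---|---|---|---|---|
| 0.25 | 2-fold | 0.1% | 5% | 35% |
| 0.50 | 2-fold | 98% | 93% | 63% |
| 0.33 | 3-fold | 98% | 98% | 93% |

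At CV 40% and g = 0.40, the chance that any of 6 exceeds now is 5%. After a 2-fold step 28% of subjects exceed, and the chance of at least one of 6 is 86%. After a 3-fold step 68% of subjects exceed.

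**5. Repeat dosing.** The MAD cap is on dose. Under linear kinetics the accumulation ratio is 1/(1 − 2^(−24/t½)). For assumed half-lives of 12, 24 and 36 hours it is 1.33, 2.00 and 2.70, so a dose that stayed within the AUC limit once need not do so on Day 14.

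**The case against.** The best defence is that 3.5.2 itself forbids the outcome described. The reviewers have Cmax and AUC0-24 and know the step, so a proportional projection is one multiplication. Under 3.2 the DSMB may adjust the dose on PK grounds. Its operations sit in a separate Data and Safety Monitoring Plan that is not supplied and may describe projection. Because 3.5 cross-refers to 3.5.2, its word *reached* can also be read as the forward-looking condition having been met. All of this is fair: authority to act exists, and absence from SAP 10 does not show that nobody will project. It does not supply a method, although 8.6 sends the detail of the interim analyses to the SAP.

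Four stronger readings are tempting and not supported.
- *Interim PK is optional.* That is true only of the wording of 8.6. Protocol 3.3.1 and 3.5 require an acceptable PK analysis, and SAP 10 says results will be generated for SAD and MAD. This is a conflict to reconcile.
- *Nothing else limits exposure.* The step cap, sentinel dosing, the MAD cap at the highest SAD dose, the Smoker cap at the highest MAD dose and intermediate-dose adjustment all help. They limit dose or the number exposed, so they do not substitute for the numeric limit. The Smoker cap does reduce the consequence of leaving Part C out of SAP 10.
- *The probabilities forecast this trial.* They assume a CV, a slope and a starting point, and that reviewers take the full step regardless. The 0.25 row shows how far they depend on these.
- *The Part A list lacks the metric it needs.* Only the dose-normalised AUC0-24 is absent; AUC0-24 itself is listed.

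On individual versus mean, the phrase about exposures in subjects leans towards individuals, but no statistic is named.

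**Conclusion.** The point holds. The rule looks forward, the specified interim output looks back, and 3.5 and 3.5.2 differ on whether escalation stops once the limit is reached or before. That conclusion needs no numerical assumption. Its size does: at slope 1, means at 50% to 100% of the limit (2-fold step) or 33% to 100% (3-fold step) show no breach yet project to or above the limit. For slopes of 0.8 to 1.2 the lower edges are 57% to 44% and 42% to 27%. The breach probabilities are illustrations only.

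The conflict over whether interim PK is required, and the omission of Part C from SAP 10, are established from the text alone. With the required PK analysis in 3.3.1 and 3.5, the other dose controls and the unseen monitoring plan, this should be fixed but does not rank as a must-fix.

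**What to change.** 1. **SAP 10, projection.** Add to each escalation package the projected Cmax and AUC0-24 at the next proposed dose, with an individual upper prediction limit, beside 25.4 and 224. A power-model slope cannot be estimated after Cohort A1 and is fragile after A2. Use a stated proportionality assumption with a range of slopes until at least three dose levels are available, then the power model of SAP 7.5.2. Include observed accumulation for multiple dosing.
2. **SAP 10, scope.** Name Part C.
3. **Protocol 3.5 and 3.5.2.** Reconcile *reached* with *before achieved*, and state whether the limit is read on individuals or the cohort mean.
4. **Protocol 8.6, synopsis, 3.2, 3.3.1, 3.5 and SAP 10.** Reconcile whether interim PK is required before escalation. If the monitoring plan already covers projection, cite it.

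The sponsor and DSMB choose the criterion; no dose or threshold is proposed here. The cost is one extra interim table per cohort and some wording. The downside is that early projections will be uncertain, which the range of slopes makes visible.
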